International Multicenter Double-blind Placebo-Controlled Parallel-Group Randomized Clinical Trial of Efficacy and Safety of Ergoferon in the Treatment of Viral Intestinal Infections in Children

Phase IV

Sponsor OOO «NPF «MATERIA MEDICA HOLDING»

Protocol number MMH-ER-008

Version date: November 02, 2015

ClinicalTrials.gov Id: NCT03039699

Protocol Summary

This document represents the protocol summary for the study on human subjects. The study will be carried out in accordance with ICH GCP, National Standard of the Russian Federation GOST 52379-2005 "Good Clinical Practice", Helsinki Declaration of World Medical Association, relevant requirements of the regulatory authorities as well as the study procedures.

Title of Study

International multicenter double-blind placebo-controlled parallel-group randomized clinical trial of efficacy and safety of Ergoferon in the treatment of viral intestinal infections in children.

Phase: IV

Sponsor: OOO "NPF "Materia Medica Holding", Moscow, Russia

Protocol No. MMH-ER-008

Objective of the study

• To obtain additional data on the efficacy and safety of Ergoferon in the treatment of viral intestinal infections in inpatient children.

Endpoints

Primary endpoint

1. Average diarrhea duration¹.

Secondary endpoints

- 1. Percentage of patients without diarrhea following 48, 72, and 96 hours of treatment.
- 2. Percentage of patients with recovery² following 48, 72, and 96 hours of treatment.
- 3. Average illness duration (from the enrollment to the recovery).
- 4. Total CDS score at 24, 48, and 72 hours after treatment initiation.
- 5. Average vomiting duration (if any).
- 6. Percentage of patients with negative PCR tests on Days 3, 4, 6, and 10 of observation versus baseline (no RNA detection of rotaviruses/ noroviruses/ astroviruses/ adenoviruses in patients who had positive tests at baseline).
- 7. Percentage of patients with worsening of illness³ and/or hospital-acquired infection⁴.

CONFIDENTIAL Page 2 of 14

¹ Diarrhea duration is considered as the time between receiving the first dose of investigational medicine /placebo and the normal consistency of stool pattern (to the previous stool consistency before diarrhea), i.e.

¹⁾ time to the first loose stool which is followed by two normal consistency stools over 24 h (infants may have three episodes of loose stool over a 24-hour period), or 2) time to ≤3 episodes of stool occurring over 24 h, at least 2 of which are normal consistency stools, or

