Medical history	+						
Physical examination	+	+	+	+	+	+	
Body weight measurement	+					+	
Body length/height measurement	+						
Evaluation of dehydration symptoms using CDS	+	+	+	+	+	+	
Diary supply	+						
Checking the correctness of filling the diary		+	+	+	+	+	
Parent/adopter inquiry (personal/by phone) and filling questionnaire "Parent's/adopter's inquiry data"							+
Return of patient diary						+	
Concomitant therapy	+	+	+	+	+	+	+
Eligibility assessment	+						
Obtaining stool sample for PCR diagnosis	+		+	+		+	+*
Safety laboratory tests (hematology, serum chemistry,	+					+	

CONFIDENTIAL Page 9 of 14

urinalysis)							
Randomization and prescription of study drug	+						
Study drug supply							
, , , , , , , , , , , , , , , , , , ,	T .						
Basic medication supply	+	+	+	+	+		
Study drug accountability,						+ **	+ **
compliance assessment						Į.	!
Evaluation of treatment safety	+	+	+	+	+	+	+

^{*} All the subjects will receive sterile containers for stool storage and transportation on day 10. In case of a phone visit on day 10 stool samples will be delivered to the local laboratory by a courier.

Statistical Analyses.

Samples

Total set: all patients included in the study whose parents/adoptive parents signed the Informed Consent Form for the patient's participation in the study. All AEs including those occurred prior to the study therapy will be considered throughout the study for this sample.

Safety population: all patients who received at least one dose of the study drug. This sample will be used to *analyze the study treatment safety and tolerability*, since all the AEs identified after the study product administration will be recorded.

Full Analysis Set. This sample includes all enrolled and randomized patients, except for those who have experienced at least one of the following events:

- 1) non-compliance with inclusion / exclusion criteria;
- 2) the patient has not taken a single dose of the study drug;
- 3) lack of any data of the patient following randomization;
- 4) withdrawal of a patient due to early discharge (discharge of patient with persistent symptoms of acute intestinal infections on days 2-5 of hospitalization before the study treatment is completed at the parent's/adopter's request).

This sample is the most consistent with the "Intention-to-treat" principle, will be used for the *Intention-to-treat analysis (ITT analysis) of the the study therapy efficacy*.

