¹¹ According to the report for multicenter double-blind placebo-controlled parallel-group randomized clinical study of therapeutic efficacy and safety of anti-IFN at rotavirus infection in children (phase III), mean diarrhea duration in active product group was 1.9±1.2 days, in Placebo group - 2.9±1.8 days.

The application of parametric criteria will be accompanied by a check for normality of the compared samples (Kolmogorov-Smirnov test).

The following parametric methods and approaches are supposed to be used:

- 1. To assess the differences of continuous variables obtained in two different (independent) groups –Student t-test for independent samples.
- To assess the differences of continuous variables obtained in one group at two different visits – Student t-test for for paired samples.
- 3. To assess the temporal dynamics of the compared indicators analysis of variance (ANOVA) or covariance (ANCOVA) in the modification with repeated measures.
- 4. In case of multiple comparisons between the groups will apply a variety of corrections for multiplicity Dunnett, Tukey, Scheffe, Holm adaptive test, etc.
- 5. In case of abnormal data distribution, approaches with the Generalized Linear Models and / or Mixed Linear Models will be used.
- 6. Selection of the type of distribution, clarification of the factor and covariance structures of the model is carried out with fit statistics such as AIC (Akaike information criterion).

To perform the above-mentioned statistical tests and techniques, it is assumed that the following SAS procedures are used:

- UNIVARIATE check for normality of the compared distributions;
- CORR, MEANS calculation of descriptive statistics;
- TTEST Student t-test with all the modifications;
- GLM analysis of Generalized Linear Models for studying temporal dynamics (ANOVA, ANCOVA);
- GENMOD analysis of Generalized Linear Models.
 MIXED analysis of Generalized Linear Models.

Non-parametric criteria

Below, there are the main types of possible comparisons with the respective criteria:

- 1. To assess the differences of continuous variables obtained in two different (independent) groups Mann-Whitney U-test.
- 2. To assess the temporal dynamics of the compared indicators Friedman test, non-parametric analogue of analysis of variance with repeated measures.

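### For secondary endpoint 4 (CDS at 24, 48 and 72 h) the plan does not require adjustment for the Day 1 CDS; adjusting would usually add useful power at almost no cost

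*Combined protocol and SAP*

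**What the plan says.** All places are in the combined protocol and SAP.

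- **Endpoint.** Secondary endpoints, item 4: "Total CDS score at 24, 48, and 72 hours after treatment initiation".
- **Data collected.** The Schedule of study procedures has a row "Evaluation of dehydration symptoms using CDS", marked for Days 1 to 6. Inclusion criterion 3 requires a CDS of at least 1 and exclusion criterion 4 removes scores of 7 or more, so entry scores run from 1 to 6.
- **Method for time courses.** Parametric criteria, item 3: "To assess the temporal dynamics of the compared indicators analysis of variance (ANOVA) or covariance (ANCOVA) in the modification with repeated measures". The SAS list below it gives GLM the role "analysis of Generalized Linear Models for studying temporal dynamics (ANOVA, ANCOVA").
- **Other listed routes.** Item 1 gives the t-test for independent groups. Item 5 says: "In case of abnormal data distribution, approaches with the Generalized Linear Models and / or Mixed Linear Models will be used". Item 6 leaves the covariance structure to fit statistics. Under Non-parametric criteria, item 1 is the Mann-Whitney test and item 2 the Friedman test.
- **Gate between routes.** "The application of parametric criteria will be accompanied by a check for normality of the compared samples (Kolmogorov-Smirnov test").

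No passage assigns CDS to one of these routes, names Day 1 CDS as a covariate, or says which term or time point carries the conclusion for endpoint 4.

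**The concern.** Children enter with a CDS anywhere from 1 to 6, and a child who starts higher is likely to be higher a day or two later. That between-child spread is noise in the arm comparison, and the recorded Day 1 score can remove part of it. The t-test, the Mann-Whitney test and repeated-measures ANOVA on the post-treatment scores all leave it in.

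ANOVA with Day 1 among the repeated outcomes is also open under item 3, and is weaker still. Treatment cannot have changed the Day 1 score, so it dilutes the main effect, and the treatment-by-time test becomes an overall comparison of curves instead of an arm difference at the three named times.

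At stake is whether a real CDS difference is detected, and whether the method is fixed before the data are seen. Diarrhea duration, the primary endpoint, is not a repeated score and is not affected.

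**Working it through.** **Step 1. The plan's sample size.** Inputs from Evaluation of sample size: difference 12 h, SD 36 h, two-sided 5%, power 80%.

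n = 2 × (1.960 + 0.842)² × 36² / 12² = 141.3 per arm. An assumed two-look O'Brien-Fleming inflation of about 1.008 gives 142.4, so 143. Then 286 / (1 − 0.5) = 572. The stated figures reproduce. They concern diarrhea duration; there is no power statement for CDS. I carry 143 per arm forward.

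**Step 2. What adjustment does, by formula.** If ρ is the correlation between Day 1 CDS and the later outcome, adjustment multiplies the residual SD by √(1 − ρ²). Power ≈ Φ(λ/√(1 − ρ²) − 1.96), where λ = (difference/SD) × √(n/2).

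Take a difference of 0.333 SD, borrowed from the primary endpoint as an assumption: λ = 0.333 × √71.5 = 2.82. At 48 h:

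| ρ with Day 1 | Formula | Simulated |
|---|---|---|
| unadjusted | 80% | 79-81% |
| 0.25 | 83% | 81% |
| 0.50 | 90% | 90% |
| 0.81 | 99.8% | 99.7% |

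**Step 3. Including Day 1 as an outcome.** Take the same effect at all three later times, equal SDs and correlation 0.5 throughout.

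- Adjusted mean of the three times: residual variance 0.667 − 0.25 = 0.417; 2.82/√0.417 = 4.37; power 99%.
- Unadjusted mean of the three times: 2.82/√0.667 = 3.45; power 93%.
- ANOVA main effect over four visits: the effect shrinks to 0.75 × 2.82 = 2.11 and the variance of the mean is 0.625; 2.11/√0.625 = 2.67; power 76% (simulated 76%).
- Treatment-by-time test: simulated 84%.

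**Step 4. CDS-like data.** Integer scores, entry 1-6, 143 per arm, 30% faster recovery, nothing missing. All distributions are assumed.

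| Analysis | Power over six settings | One setting |
|---|---|---|
| Adjusted 24-72 h mean | 32-99% | 71% |
| Same mean, unadjusted | 22-86% | 52% |
| ANOVA with Day 1, main effect | 15-45% (with row below) | 29% |
| ANOVA with Day 1, corrected interaction | 15-45% (with row above) | 28% |

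Adjustment was ahead in every setting, by about 9 to 29 points over the unadjusted mean. A separate run over nine assumption sets gave 44-84% adjusted against 39-64% for ANOVA on the three times only, a gap of 5 to 28 points.

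The 71% against 52% implies (1.96 + 0.55)/(1.96 + 0.05) = 1.25, so √(1 − ρ²) = 0.80 and ρ = 0.60. From the same 52%, ρ = 0.3 would give 2.01/0.954 = 2.11, or 56%; ρ = 0.8 would give 2.01/0.6 = 3.35, or 92%.

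**Step 5. Type I error at nominal 5%.**

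- Uncorrected treatment-by-time F with Day 1 as an outcome, four visits: mostly about 6-7%; 8.1% under the most uneven covariance tried; about 5% under compound symmetry.
- The same test with six visits: 6.8-9.4%. One further family of assumptions gave 7-11%.
- Greenhouse-Geisser or multivariate version: 4.5-5.7%. Main effect: 4.5-5.7%.
- ANOVA on the three endpoint times only: 4.3-5.6% (uncorrected interaction), 4.0-5.3% (main effect).
- Adjusted analysis: 4.4-5.6%, apart from one setting at 6.7% in a separate family of runs.

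**The case against.** **The normality check may take CDS off item 3.** This largely stands. An integer score crowding towards 0 will nearly always fail Kolmogorov-Smirnov at this size; in simulation it failed at all three times in every one of 100 arms. But the destinations do not settle the matter. Item 5 names model families without terms. Mann-Whitney is unadjusted. Friedman compares visits within children and does not by itself test the arms.

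**The plan already lists the tools.** ANCOVA is in the quoted sentence, MIXED is in the procedure list, and item 6 says that "clarification of the factor and covariance structures of the model is carried out with fit statistics such as AIC (Akaike information criterion"). True, and the document calls itself a protocol summary. Still, permission to use ANCOVA is not a commitment to adjust for Day 1 CDS, and a fit statistic does not choose the arm contrast.

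**Stronger readings that a reader might infer, and that the documents do not support:**

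- *That the plan inflates type I error.* This needs Day 1 as an outcome, an uncorrected F test and unequal covariances together. The text prescribes neither of the first two.
- *That power falls from 75% to 41%.* Such a contrast arises if a six-visit ANOVA main effect is set against an adjusted 24-72 h mean. It mixes the time window with the adjustment. Step 4 keeps the window the same.
- *That no estimate at the three times is available.* The t-test and Mann-Whitney routes compare the arms at each visit, and Data presentation promises confidence intervals for comparisons that support a conclusion.
- *That ANOVA and GLM should go altogether.* Item 3 covers every indicator followed over time; one secondary endpoint does not justify that.

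The gain also depends on ρ. With ρ near 0.3 it is only a few points. At correlation 0.9 the treatment-by-time test lost nothing (over 99%), although the ANOVA main effect fell to 60%. The adjusted analysis's single 6.7% came from 2,000 trials, where the Monte Carlo standard error is √(0.05 × 0.95/2000) = 0.5 points. Chance does not easily explain it, so type I error is no argument for either side.

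**Conclusion.** The point holds as one of analysis choice for a secondary endpoint. The plan permits several analyses of endpoint 4 and requires none to use the Day 1 CDS. Under the assumed data, adjustment on the same 24-72 h window gains about 9 to 29 points of power (5 to 28 in the second set of assumptions). The gain is larger against an ANOVA that treats Day 1 as an outcome, which is a permitted form and not a stated rule. The excess type I error belongs to one uncorrected test and is modest.

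The sizes rest on assumed CDS means, SDs, recovery rates and treatment effect, with no missing scores. The direction needs only that Day 1 CDS predicts later CDS. The change is worth making because it is cheap and fixes the method in advance.

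**What to change.** For endpoint 4 only, add to the statistical section:

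- Outcomes are CDS at 24, 48 and 72 h, analysed in PROC MIXED.
- Fixed effects are arm, time, arm-by-time, Day 1 CDS and Day 1 CDS-by-time.
- Within-child covariance is unstructured (three variances and three covariances), so no AIC choice is needed here.
- Day 1 CDS is a covariate and never an outcome.
- Report the arm difference with 95% CI at each of the three times and for their average.
- Use this model whatever the Kolmogorov-Smirnov result; with 143 per arm, contrasts of means do not depend on normal scores.

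Item 3 and GLM may stay for other indicators.

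The cost is wording. Day 1 CDS is already recorded and MIXED is already listed, so no data, patients or software are added. The small downside is that adjusted means have to be shown beside the raw means.
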